14.0 BIOSTATISTICS

The historical control leak rate at our institution among patients receiving partial, total gastrectomy or esophagectomy is 8-15%: esophagectomy leak rate of around 15% and total and proximal gastrectomy leak rate of around 10%. A weighted average of 13% between the groups will be considered an unacceptable leak rate. We will employ Simon's two stage design to show a decrease in the leak rate assessed radiographically and clinically from 13% to 5% which would require 86 total patients to detect this difference with type I and II error rates of 10% each. In the first stage we will enroll 43 patients and if 5 patients experience a leak, then the study will be terminated, however if only 4 or less patients experience a leak then we will proceed to accruing up to 86 patients. If at the end of the second stage we see 7 or less leaks then we will consider the study worthy of further investigation. We expect two thirds of the accrued patients to have total gastrectomy performed while the rest to receive esophagectomy. Exact 95% confidence intervals will be computed for the leak rate for all the patients as well as separately for esophagectomy and total gastrectomy.

Similarly, the stricture rate will be estimated using binomial proportions and exact 95% CI will be computed.

The different cost metrics will be summarized descriptively: continuous cost metrics will be summarized using medians and ranges while binary variables will be summarized using binomial proportions.

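### Does the planned exact 95% interval for the leak rate undermine the 7-of-86 success rule?

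*Combined protocol and SAP*

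**What the plan says.** All the relevant text is in Section 14.0 (Biostatistics) of the combined protocol and SAP.

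- Null rate: "A weighted average of 13% between the groups will be considered an unacceptable leak rate". The alternative is 5%.
- Design: "We will employ Simon's two stage design to show a decrease in the leak rate", "which would require 86 total patients to detect this difference with type I and II error rates of 10% each".
- Interim rule after 43 patients: "if only 4 or less patients experience a leak then we will proceed to accruing up to 86 patients"; five leaks end the study (read here as five or more).
- Final rule: "If at the end of the second stage we see 7 or less leaks then we will consider the study worthy of further investigation".
- Estimation: "Exact 95% confidence intervals will be computed for the leak rate for all the patients as well as separately for esophagectomy and total gastrectomy".

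The section does not name the exact method, does not say whether the interval allows for the two stages, and gives the interval no role in the decision. The stricture rate gets the same kind of interval, with no hypothesis attached.

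**The concern.** The trial has one arm, so comparison with 13% is its whole evidential basis. The rule is one-sided at 10% and built on two-stage sampling. The interval is two-sided at 95% and, if computed in the usual way, treats the 86 patients as a single fixed sample. At three of the eight passing counts (0 to 7) a positive verdict would appear beside an interval that does not exclude the unacceptable rate, and the plan does not say how to present that.

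There is a second worry. A trial that reaches 86 patients has already survived the interim look, so its raw leak proportion could be too low. If both points held, readers might doubt whether the primary objective was met, and the reported rate might favour the device.

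**Working it through.** **Inputs (Section 14.0).** p0 = 13%, p1 = 5%, both error rates 10%, n1 = 43, continue at 4 or fewer leaks, N = 86, success at 7 or fewer. Assumption: the exact interval is Clopper-Pearson with n = 86.

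**1. Reproduce the design.** Let F(k, p) be the probability of continuing and ending with at most k leaks:

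F(k, p) = sum over x = 0 to min(4, k) of Bin(x; 43, p) × P[Bin(43, p) ≤ k − x].

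- F(7, 0.13) = 0.0989, the type I error.
- F(7, 0.05) = 0.9012, so the type II error is 1 − 0.9012 = 0.0988.

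Both are within 10%. A search over N from 55 to 99 gives 43/86 with cut-offs 4 and 7 as the Simon optimal design (expected N 57.05 at 13%).

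**2. Upper limits by final count.** The ordinary limit solves P[Bin(86, p) ≤ k] = a. The two-stage limit solves F(k, p) = a. Here a = 0.025 for the upper end of a 95% interval and a = 0.10 for a one-sided 90% bound.

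| Leaks of 86 | Rule | F(k, 0.13) | Ordinary 95% | Two-stage 95% | Ordinary one-sided 90% | Two-stage one-sided 90% |
|---|---|---|---|---|---|---|
| 4 | success | 0.0094 | 11.48% | 11.48% | 9.08% | 9.08% |
| 5 | success | 0.0253 | 13.05% | 13.02% | 10.52% | 10.49% |
| 6 | success | 0.0549 | 14.57% | 14.44% | 11.92% | 11.79% |
| 7 | success | 0.0989 | 16.05% | 15.75% | 13.31% | 12.98% |
| 8 | failure | 0.1523 | 17.51% | 16.91% | 14.67% | 14.02% |

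The third column explains the overlap. At 5, 6 and 7 leaks the tail probability under 13% lies between 0.025 and 0.10, so these counts pass a 10% test and fail a 2.5% test. Allowing for the stages but keeping 95% leaves all three limits above 13%. Moving to 90% without allowing for the stages clears 5 and 6 leaks and leaves only 7, at 13.31%. The level therefore accounts for nearly all of the overlap. At 5 leaks the excess over 13% is 0.05 percentage points.

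**3. How often it happens.** At a true 5%, the probabilities of ending with 5, 6 or 7 leaks after continuing are 0.1660 + 0.1091 + 0.0572 = 0.332 after rounding, which is 0.332 / 0.901 = 37% of successes. At a true 13%, these counts supply 8.95 of the 9.89 percentage points of false success.

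**4. Is the ordinary interval valid?** Sum the probabilities of all outcomes whose interval contains p, using n = 43 for trials that stop and n = 86 for those that finish. Coverage is 98.0% at p = 3%, 96.5% at 5%, 95.2% at 10%, 97.1% at 13% and 96.0% at 15%.

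**5. Bias of the raw proportion.**

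| True rate | P(reach stage 2) | Mean raw rate given stage 2 | Mean raw rate, all trials |
|---|---|---|---|
| 5% | 93.8% | 4.75% | 5.24% |
| 13% | 32.7% | 10.2% | 13.9% |

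The standard unbiased two-stage estimate is E[X1/43 | total, X1 ≤ 4], where X1 is the stage 1 leak count. At 7 leaks it is 7.0%, below the raw 7/86 = 8.1%.

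**The case for a change.** The case for a change has force. The overlap is likely at the design's own target rate. At 7 leaks, ignoring the stages disagrees with the rule even at the rule's own level: the fixed-sample tail probability is 0.115 against the two-stage 0.0989. Section 14.0 offers no other inferential summary of the leak rate. One added sentence would give a bound that falls below 13% exactly when the rule declares success, and would remove any temptation to choose afterwards between a positive rule and an inconclusive interval.

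The arithmetic stands. So does the observation that the section neither names the interval method nor warns of the overlap. The inference that a change is needed does not follow. The count rule is explicit, so there is nothing to choose between: a reader who sees 6 leaks knows the criterion was met. Passing claims only that the approach merits further study, and an interval reaching above 13% beside that modest claim shows honestly how much 86 patients can establish. A bound that falls below 13% exactly when the count is 7 or fewer carries no new verdict.

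The bias argument is true only conditionally. Completed trials do read low when the true rate is high, but only 32.7% of trials get that far at 13%. Over all trials the raw rate errs upward, against the device. Substituting the unbiased estimate would lower the reported rate at 7 leaks, which is the reverse of what the worry calls for.

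**Conclusion.** The concern does not call for a change. Followed as written, the plan gives a decision with the stated error rates (0.0989 and 0.0988) and an interval with at least nominal coverage. The overlap at 5 to 7 leaks, seen in 33.2% of trials at a true 5%, is the ordinary consequence of screening at one-sided 10% while describing at 95%, and that is a fair trade-off. No result, sample size or conclusion would differ under a matched bound.

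An analyst may reasonably name the interval method, note that the count governs, and show the two-stage 90% bound beside the 95% interval (10.5%, 11.8% and 12.98% at 5, 6 and 7 leaks). That is a reporting preference.

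This rests on three readings: the exact interval is Clopper-Pearson, a stage 1 stop means five or more leaks, and 13% is taken as the plan states it. Whether 13% is the right average of the two procedure-specific rates is a separate question.

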15.1 RESEARCH PARTICIPANT REGISTRATION AND RANDOMIZATION PROCEDURES

15.2 Research Participant Registration

Confirm eligibility as defined in the section entitled Criteria for Patient/Subject Eligibility.

Obtain informed consent, by following procedures defined in section entitled Informed Consent Procedures.

During the registration process registering individuals will be required to complete a protocol specific Eligibility Checklist.

All participants must be registered through the Protocol Participant Registration (PPR) Office at Memorial Sloan-Kettering Cancer Center. PPR is available Monday through Friday from 8:30am – 5:30pm at [contact]. Registrations must be submitted via the PPR Electronic Registration System (<http://ppr/>). The completed signature page of the written consent/RA or verbal script/RA, a completed Eligibility Checklist and other relevant documents must be uploaded via the PPR Electronic Registration System.

15.3 Randomization

N/A

16.1 DATA MANAGEMENT ISSUES

A Research Study Assistant (RSA) will be assigned to the study. The responsibilities of the RSA include project compliance, data collection, abstraction and entry, data reporting,

regulatory monitoring, problem resolution and prioritization, and coordinating the activities of the protocol study team.

The data collected for this study will be entered into an institutionally registered database. Source documentation will be available to support the computerized patient record.

16.2 Quality Assurance

Monthly registration reports will be generated to monitor patient accruals and completeness of registration data. Routine data quality reports will be generated to assess missing data and inconsistencies. Accrual rates and extent and accuracy of evaluations and follow-up will be monitored periodically throughout the study period and potential problems will be brought to the attention of the study team for discussion and action. Random-sample data quality and protocol compliance audits will be conducted by the study team, at a minimum of two times per year, more frequently if indicated.

16.3 Data and Safety Monitoring

The Data and Safety Monitoring (DSM) plans at Memorial Sloan-Kettering Cancer Center were approved by the National Cancer Institute in September 2001. The plans address the new policies set forth by the NCI in the document entitled "Policy of the National Cancer Institute for Data and Safety Monitoring of Clinical Trials" which can be found at: <http://cancertrials.nci.nih.gov/researchers/dsm/index.html>. The DSM Plans at MSKCC were established and are monitored by the Office of Clinical Research. The MSKCC Data and Safety Monitoring Plans can be found on the MSKCC Intranet at: <http://mskweb2.mskcc.org/irb/index.htm>

There are several different mechanisms by which clinical trials are monitored for data, safety and quality. There are institutional processes in place for quality assurance (e.g., protocol monitoring, compliance and data verification audits, therapeutic response, and staff education on clinical research QA) and departmental procedures for quality control, plus there are two institutional committees that are responsible for monitoring the activities of our clinical trials programs. The committees: Data and Safety Monitoring Committee (DSMC) for Phase I and II clinical trials, and the Data and Safety Monitoring Board (DSMB) for Phase III clinical trials, report to the Center's Research Council and Institutional Review Board. During the protocol development and review process, each protocol will be assessed for its level of risk and degree of monitoring required. Every type of protocol (e.g., NIH sponsored, in-house sponsored, industrial sponsored, NCI cooperative group, etc.) Will be addressed and the monitoring procedures will be established at the time of protocol activation.

17.1 PROTECTION OF HUMAN SUBJECTS

Participation in this trial is voluntary. All patients will be required to sign a statement of informed consent, which will conform to MSKCC IRB guidelines.

1. Risks to the Subjects

Human Subjects Involvement and Characteristics: All patients at MSKCC who meet the inclusion criteria will be eligible. 86 patients will be entered on the trial; patients will be 18 years of age or older. Both men and women and members of all ethnic groups are eligible for this trial. This protocol does not include children because the number of otherwise eligible children is expected to be low. This statement is based on exclusion 4b of the NIH Policy and Guidelines on the Inclusion of Children as Participants in Research Involving Human Subjects.

2. Adequacy of protection against risks

Consent process:

All patients at MSKCC and participating sites who meet the inclusion criteria will be eligible. Participation in the trial is voluntary. All patients will be required to sign a statement of informed consent, which must conform to institutional IRB guidelines. Per MSKCC Policy, an IRB approved Consenting Professional listed on the face page of this trial will conduct the consent discussion with the patient and obtain written informed consent. The informed consent procedure is described in Section 18.

Possible Toxicities/Adverse Effects:

There are no known additional risks of Gentrix devices as described in Section 11.0.

Costs:

Gentrix PSM will be provided to Memorial Sloan-Kettering by ACell. Patients will not receive any compensation for participation in the study. In addition, subjects will not incur any additional costs as a result of participation in the study.

Alternatives:

The alternative to this trial is to have surgery without use of the Gentrix PSM, or have no surgery.

Confidentiality:

Every effort will be made to maintain patient confidentiality. Research and hospital records are confidential. Patients' names and any other identifying information will not be used in reports or publications resulting from this study. Other authorized agencies and appropriate personnel (e.g. qualified monitors from MSKCC) may review patient records as required.

Patient safety:

Patients are monitored by physicians and nurses during the post-operative period. In the case of an adverse reaction, immediate medical attention is available. In the evenings and weekends, we have a 24-hour urgent care facility, for outpatients. The PI will also be available at all times to organize any necessary intervention.

Monitoring of data to ensure safety:

This study will be monitored according to MSKCC and Department of Surgery Policies by the institutional IRB. The analysis of safety will include patient case review and

regulatory binder review. Adverse events, including all toxic effects of treatment, will be tabulated individually and summarized by severity and causality.

3. Potential benefits of the proposed research to the subjects and others

This trial aims to lower the leak and stricture rate in patients undergoing esophagectomy and Total Gastrectomy patients. Initial pilot data here at MSKCC suggests that there is a benefit of reinforcing the anastomosis with Gentrax PSM.

17.2 Privacy

MSKCC's Privacy Office may allow the use and disclosure of protected health information pursuant to a completed and signed Research Authorization form. The use and disclosure of protected health information will be limited to the individuals described in the Research Authorization form. A Research Authorization form must be completed by the Principal Investigator and approved by the IRB and Privacy Board (IRB/PB).

17.3 Serious Adverse Event (SAE) Reporting

An adverse event is considered serious if it results in ANY of the following outcomes:

- Death
- A life-threatening adverse event
- An adverse event that results in inpatient hospitalization or prolongation of existing hospitalization
- A persistent or significant incapacity or substantial disruption of the ability to conduct normal life functions
- A congenital anomaly/birth defect
- Important Medical Events (IME) that may not result in death, be life threatening, or require hospitalization may be considered serious when, based upon medical judgment, they may jeopardize the patient or subject and may require medical or surgical intervention to prevent one of the outcomes listed in this definition

Note: Hospital admission for a planned procedure/disease treatment is not considered an SAE.

SAE reporting is required as soon as the participant signs consent. SAE reporting is required for 30-days after the participant's last investigational treatment or intervention. Any events that occur after the 30-day period and that are at least possibly related to protocol treatment must be reported.

If an SAE requires submission to the IRB office per IRB SOP RR-408 'Reporting of Serious Adverse Events', the SAE report must be sent to the IRB within 5 calendar days of the event. The IRB requires a Clinical Research Database (CRDB) SAE report be submitted electronically to the SAE Office as follows:

For IND/IDE trials: Reports that include a Grade 5 SAE should be sent to [contact]. All other reports should be sent to [contact].

For all other trials: Reports that include a Grade 5 SAE should be sent to [contact]. All other reports should be sent to [contact].

The report should contain the following information:

Fields populated from CRDB:

- Subject's initials Medical record number
- Disease/histology (if applicable)
- Protocol number and title

Data needing to be entered:

- The date the adverse event occurred
- The adverse event
- The grade of the event
- Relationship of the adverse event to the treatment (drug, device, or intervention)
- If the AE was expected
- The severity of the AE
- The intervention
- If an amendment will need to be made to the protocol and/or consent form
- Detailed text that includes the following
 - A explanation of how the AE was handled
 - A description of the subject's condition

Indication if the subject remains on the studyThe PI's signature and the date it was signed are required on the completed report.

17.2.1 ACell SAE Reporting

SAE Reporting

For non-MSKCC sites, all SAEs will be first reported to MSKCC.

Following reporting of SAEs to MSKCC, MSKCC will then report all SAEs to ACell.

ACell Quality Assurance ([contact], [contact], [contact], [contact]) is to be notified of **any** serious device-related adverse event within 24 hours of the Investigator's awareness of the event.

Relationship of AEs

For any adverse event recorded/described, the Investigator shall indicate, to the best of his/her knowledge, an assessment of the relationships between the AE and device and between the AE and procedures according to the following definitions:

Relationship to Device

- **Unrelated**: There is no relationship between the AE and the investigational device product. This may include but is not limited to the incident being an expected outcome of a previously existing or concurrent disease, concomitant medication or procedure the subject experienced.
- **Possible**: There is no clear relationship between the AE and the study device; however, one cannot definitely conclude that there is no relationship.
- **Probable**: While a clear relationship to the device under investigation cannot be established, the AE is associated with an expected AE or there is no other medical condition or intervention, which could explain the occurrence of such an event.
- **Definite**: The relationship of the AE and the study device can definitely be established.

Relationship to Procedures

- **Unrelated**: There is no relationship between the AE and the procedure. This may include but is not limited to the incident being an expected outcome of a previously existing or concurrent disease, concomitant medication or procedure the subject experienced.
- **Possible**: There is no clear relationship between the AE and the procedure; however, one cannot definitely conclude that there is no relationship.
- **Probable**: While a clear relationship to the procedure cannot be established, the AE is associated with an expected AE or there is no other medical condition or intervention, which could explain the occurrence of such an event.
- **Definite**: The relationship of the AE and the procedure can definitely be established.

18.1 INFORMED CONSENT PROCEDURES

Before protocol-specified procedures are carried out, consenting professionals will explain full details of the protocol and study procedures as well as the risks involved to participants prior to their inclusion in the study. Participants will also be informed that they are free to withdraw from the study at any time. All participants must sign an IRB/PB-approved consent form indicating their consent to participate. This consent form meets the requirements of the Code of Federal Regulations and the Institutional Review Board/Privacy Board of this Center. The consent form will include the following:

1. The nature and objectives, potential risks and benefits of the intended study.
2. The length of study and the likely follow-up required.

3. Alternatives to the proposed study. (This will include available standard and investigational therapies. In addition, patients will be offered an option of supportive care for therapeutic studies.)
4. The name of the investigator(s) responsible for the protocol.
5. The right of the participant to accept or refuse study interventions/interactions and to withdraw from participation at any time.

Before any protocol-specific procedures can be carried out, the consenting professional will fully explain the aspects of patient privacy concerning research specific information. In addition to signing the IRB Informed Consent, all patients must agree to the Research Authorization component of the informed consent form.

Each participant and consenting professional will sign the consent form. The participant must receive a copy of the signed informed consent form.

